5.9.3. Data Monitoring Committee

There will be no Data Monitoring Committee in this study.

5.10. Total Blood Volume

The total blood volume to be collected for each patient enrolling in this study for treatment with fremanezumab is approximately 205.5 mL for scheduled tests. An additional 30 mL of blood may be collected in the event of follow-up for liver enzymes as detailed in [Appendix J](#).

The total blood volume to be collected for each patient enrolling in this for evaluation of ADAs, fremanezumab concentrations, and safety (adverse events and concomitant medications) is approximately 9 mL.

Details are provided in [Appendix L](#).

6. ASSESSMENT OF EFFICACY

6.1. Assessments of Efficacy

There is no primary efficacy measure.

6.2. Electronic Diary Device

Efficacy endpoints related to CH attacks will be derived from data collected daily using an electronic diary device. Eligible patients will receive comprehensive training at screening from the investigational site personnel on the use of the electronic diary device. Investigational site personnel will also instruct patients on the requirement for timely and daily completion of the electronic diary.

Patients will complete electronic headache diary entries with questions about the previous day, starting from the day after the screening visit through the end of treatment (EOT)/early withdrawal visit. The electronic headache diary device will allow entry of headache information for up to 2 days after a given day.

Patients who report a CH attack will answer questions about the attack (ie, occurrence and number of CH attacks, duration of CH attack[s], severity of CH attack[s], and acute CH-specific medication and oxygen use).

Patients will be asked about their performance at work or at school on CH attack-free days. Additional details can be found in the electronic diary device training manual.

If a patient fails to complete the diary for the preceding day, the patient will be prompted to enter the missed day's information the next time he/she accesses the electronic diary provided no more than 2 days have elapsed since completion of that day. If more than 2 days have elapsed since completion of a diary day, the patient will not be allowed to enter diary information for that day, and it will be considered a missed day.

If a CH is reported, then CH intensity will be subjectively rated by the patient as follows:

- Mild
- Moderate
- Severe
- Very severe

6.3. Hospital Anxiety and Depression Scale

The HADS is a validated and reliable, 14-item scale developed by [Zigmond and Snaith \(1983\)](#) to measure anxiety (7-items) and depression (7-items). Each item is scored on a 4-point scale from 0 to 3. Scores for depression and anxiety range from 0 to 21; a score of 0 to 7 is normal, 8 to 10 is borderline abnormal, and 11 to 21 is abnormal.

Patients will complete the HADS at the time points detailed in [Table 4](#). Responses will be recorded in the site tablet.

6.4. EuroQol-5 Dimension Questionnaire

The 5-level EQ-5D (EQ-5D-5L) is a standardized questionnaire that assesses overall state of health. The EQ-5D-5L consists of 2 parts. In part 1, patients rate their health state in 5 domains: mobility, self-care, usual activities, pain/discomfort, and mood using a scale of 1 to 5, where 1 = no problems, 2 = slight problems, 3 = moderate problems, 4 = severe problems, and 5 = extreme problems. In part 2, patients rate their health state on a 100 mm visual analog scale; a rating of 0 represents the worst imaginable health state, and a rating of 100 represents the best imaginable health state.

Patients will complete the EQ-5D-5L at the time points detailed in [Table 4](#). Responses will be recorded in the site tablet.

6.5. Twelve-Item Short-Form Health Survey

The SF-12 (version 2) is a generic health survey containing 12 questions to measure functional health and well-being rated in 8 health domains (physical function, role limitations due to physical problems, bodily pain, general health perceptions, vitality, social functioning, role limitations due to emotional problems, and mental health) with 1 or 2 questions per domain. The SF-12 was developed from the 36-Item Short-Form Health Survey ([Ware et al 1996](#)). Scores range from 0 to 100, with higher scores indicating better health status.

Patients will complete the SF-12 at the time points detailed in [Table 4](#). Responses will be recorded in the site tablet.

6.6. Work Productivity and Activity Impairment Questionnaire

The generic version of the WPAI questionnaire measures the overall effect of health on productivity at work and daily activities. The specific health problems version of the WPAI questionnaire allows investigators to attribute productivity and activity impairment issues to specific health conditions. After the employment status of a respondent is identified, 3 open-ended questions are asked concerning (1) hours absent from work due to health problems (or specific condition), (2) hours absent from work due to other reasons, and (3) hours actually worked. Two additional questions are included that ask about the impact of health on productivity, 1 concerning productivity at work and the other concerning daily activities outside of work. The response format of each item of the WPAI questionnaire consists of an 11-point scale ranging from 0 (no impairment) to 10 (complete impairment) ([Reilly et al 1993](#)).

Patients will complete the WPAI questionnaire at the time points detailed in [Table 4](#). Responses will be recorded in the site tablet.

6.7. Impact on Partner and Family Questionnaire

The partners/family members of patients participating in the study, if applicable, will complete an Impact on Partner and Family questionnaire at the time points detailed in [Table 4](#). Responses will be recorded in the site tablet. The questionnaire will include questions about the impact of CH on the patient's ability to do chores, the number of days that the patient missed a family or social activity since the last assessment due to CH, and the frequency with which the patient avoids making plans for family/social activities due to CH. Partners/family members will be

asked to attend the study visit with the patient or to return to the investigational center within ± 3 days of the patient's visit if unable to appear at the same time.

6.8. Patient-Perceived Satisfactory Improvement

The PPSI was developed by [ten Klooster et al \(2006\)](#) for pain intensity and was adjusted for CH symptoms improvement. Patients will mark the level of CH-associated pain and indicate if pain is “much worse,” “moderately worse,” “slightly worse,” “unchanged,” “slightly improved,” “moderately improved,” or “much improved” compared with 4 weeks ago. PPSI will be defined as the change in pain that corresponds with a minimal rating of “slightly improved.”

The PPSI will be completed at time points detailed in [Table 4](#). Responses at week 1 will be entered into the electronic diary device, and responses at all other time points will be entered into the site tablet.

6.9. Patient Global Impression of Change Scale

The PGIC scale is a validated generic tool for the assessment of overall change in the severity of illness following treatment. Patients will rate the change in their overall health and wellbeing compared with how they felt at the start of the study (the time after the patient received the first IMP dose as “much worse,” “moderately worse,” “slightly worse,” “stayed the same,” “a little better,” “moderately better,” or “much better.”

The PGIC scale will be completed at the time points detailed in [Table 4](#). Responses at week 1 will be entered into the electronic diary device, and responses at all other time points will be entered into the site tablet.

7. ASSESSMENT OF SAFETY

In this study, safety will be assessed by qualified study personnel by evaluating reported adverse events, reported anaphylaxis/hypersensitivity reactions, clinical laboratory test results, vital signs measurements, ECG findings, physical examination findings (including body weight measurements), injection site assessment results, eC-SSRS responses, and use of concomitant medication.

7.1. Adverse Events

7.1.1. Definition of an Adverse Event

Any untoward medical occurrence in a patient or clinical investigation subject administered a pharmaceutical product and which does not necessarily have to have a causal relationship with this treatment.

An adverse event can, therefore, be any unfavorable and unintended physical sign, symptom, or laboratory parameter that develops or worsens in severity during the course of this study, or significant worsening of the disease under study, or of any concurrent disease, whether or not considered related to the fremanezumab. A new condition or the worsening of a pre-existing condition will be considered an adverse event. Stable chronic conditions (such as arthritis) that are present before study entry and do not worsen during this study will not be considered adverse events.

Accordingly, an adverse event can include any of the following:

- intercurrent illnesses
- physical injuries
- events possibly related to concomitant medication
- significant worsening (change in nature, severity, or frequency) of the disease under study or other pre-existing conditions
- drug interactions
- events occurring during diagnostic procedures or during any washout phase of this study
- laboratory or diagnostic test abnormalities that result in the withdrawal of the patient from the study, are associated with clinical signs and symptoms or a serious adverse event, require medical treatment or further diagnostic work-up, or are considered by the investigator to be clinically significant.

(Note: Abnormal laboratory or diagnostic test results at the screening visit that preclude a patient from entering the study or receiving study treatment are not considered adverse events.)

Medical occurrences that begin before the 1st dose of IMP but after obtaining informed consent will be recorded on the Medical History/Current Medical Conditions section of the CRF.

7.1.2. Recording and Reporting of Adverse Events

For recording of adverse events, the study period for this study is defined as the time period from signature of the informed consent form (ICF) through the follow-up visit.

All adverse events that occur during the defined study period must be recorded on the source documentation and transcribed to the CRF, regardless of the severity of the event or judged relationship to the IMP. For serious adverse events and protocol-defined adverse events of special interest (see Section 7.1.7), the serious adverse event form must be completed and the serious adverse event or adverse event of special interest must be reported immediately (see Section 7.1.5.3.1). The investigator does not need to actively monitor patients for adverse events once the study has ended. Serious adverse events and adverse events of special interest occurring in a patient after the defined study period should be reported to the sponsor if the investigator becomes aware of them, following the procedures described in Section 7.1.5.3.1.

At each contact with the patient, the investigator or designee must question the patient about adverse events by asking an open-ended question such as, “Have you had any unusual symptoms or medical problems since the last visit? If yes, please describe”. All reported or observed signs and symptoms will be recorded individually, except when considered manifestations of a medical condition or disease state. A precise diagnosis will be recorded whenever possible. When such a diagnosis is made, all related signs, symptoms, and any test findings will be recorded collectively as a single diagnosis on the CRF and, if it is a serious adverse event, on the serious adverse event form.

The clinical course of each adverse event will be monitored at suitable intervals until resolved, stabilized, or returned to baseline; or until the patient is referred for continued care to a health care professional; or until a determination of a cause unrelated to the IMP or study procedure is made.

The onset and end dates, duration (in case of adverse event duration of less than 24 hours), action taken regarding IMP, treatment administered, and outcome for each adverse event must be recorded on the source documentation and transcribed to the CRF.

The relationship of each adverse event to IMP and study procedures, and the severity and seriousness of each adverse event, as judged by the investigator, must be recorded as described below.

Further details are given in the Safety Monitoring Plan.

7.1.3. Severity of an Adverse Event

The severity of each adverse event must be recorded as 1 of the following:

- Mild:** No limitation of usual activities
- Moderate:** Some limitation of usual activities
- Severe:** Inability to carry out usual activities

For severity grading of local tolerability (injection site erythema, induration, ecchymosis, and pain), refer to Section 7.11.

7.1.4. Relationship of an Adverse Event to the Test Investigational Medicinal Product

The relationship of an adverse event to the test IMP is characterized as follows (Table 7):

Table 7: The Relationship of an Adverse Event to the Test Investigational Medicinal Product

Term	Definition	Clarification
No reasonable possibility (not related)	This category applies to adverse events that, after careful consideration, are clearly due to extraneous causes (disease, environment, etc) or to adverse events that, after careful medical consideration at the time they are evaluated, are judged to be unrelated to the IMP.	The relationship of an adverse event may be considered “no reasonable possibility” if it is clearly due to extraneous causes or if at least 2 of the following apply: 
 • It does not follow a reasonable temporal sequence from the administration of the IMP. • It could readily have been produced by the patient’s clinical state, environmental or toxic factors, or other modes of therapy administered to the patient. • It does not follow a known pattern of response to the IMP. • It does not reappear or worsen when the IMP is re-administered.
Reasonable possibility (related)	This category applies to adverse events for which, after careful medical consideration at the time they are evaluated, a connection with the administration of IMP cannot be ruled out with certainty.	The relationship of an adverse event may be considered “reasonable possibility” if at least 2 of the following apply: 
 • It follows a reasonable temporal sequence from administration of the IMP. • It cannot be reasonably explained by the known characteristics of the patient’s clinical state, environmental or toxic factors, or other modes of therapy administered to the patient. • It disappears or decreases on cessation or reduction in dose. There are important exceptions when an adverse event does not disappear after discontinuation of the IMP, yet an IMP relationship clearly exists. • It follows a known pattern of response to the IMP.

IMP=investigational medicinal product.

7.1.5. Serious Adverse Events

For recording of serious adverse events, the study period is defined for each patient as that time period from signature of the ICF to the end of the follow-up period. Serious adverse events occurring in a patient after the end of the follow-up period should be reported to the sponsor if the investigator becomes aware of them, following the procedures described in Section 7.1.5.3.1.

7.1.5.1. Definition of a Serious Adverse Event

A serious adverse event is an adverse event occurring at any dose that results in any of the following outcomes or actions:

- results in death
- is life-threatening adverse event (ie, the patient was at risk of death at the time of the event); it does not refer to an event which hypothetically might have caused death if it were more severe
- requires inpatient hospitalization or prolongation of existing hospitalization, which means that hospital inpatient admission or prolongation of hospital stay were required for treatment of an adverse event, or that they occurred as a consequence of the event
Hospitalizations scheduled before the patient signed the ICF will not be considered serious adverse events, unless there was worsening of the preexisting condition during the patient's participation in this study.
- results in persistent or significant disability/incapacity (refers to a substantial disruption of one's ability to conduct normal life functions)
- is a congenital anomaly/birth defect
- an important medical event that may not result in death, be life-threatening, or require hospitalization, but may jeopardize the patient and may require medical intervention to prevent one of the outcomes listed in this definition

Examples of such events are intensive treatment in an emergency room or at home for allergic bronchospasm; blood dyscrasias or convulsions that do not result in hospitalization; or the development of drug dependency or drug abuse. Note: Any suspected transmission of an infectious agent via a medicinal product is considered an important medical event.

All occurrences of possible drug-induced liver injury that meet Hy's law criteria, defined as **all** of the below, must be reported by the investigator to the sponsor as a serious adverse event:

- ALT or AST increase of $\geq 3 \times$ the ULN
- total bilirubin increase of $\geq 2 \times$ ULN
- absence of initial findings of cholestasis (ie, no substantial increase of ALP)
- no other explanation for the observed abnormalities

An adverse event that does not meet any of the criteria for seriousness listed above will be regarded as a nonserious adverse event.

7.1.5.2. Expectedness

A serious adverse event that is not included in the Adverse Reaction section of the relevant reference safety information (RSI) by its specificity, severity, outcome, or frequency is considered an unexpected adverse event. The RSI for this study is the IB.

The sponsor's Global Patient Safety and Pharmacovigilance will determine the expectedness for all serious adverse events.

For the purpose of SUSAR reporting, the version of the IB at the time of occurrence of the SUSAR applies.

7.1.5.3. Reporting a Serious Adverse Event**7.1.5.3.1. Investigator Responsibility**

To satisfy regulatory requirements, all serious adverse events that occur during the study, regardless of judged relationship to administration of the test IMP, must be reported to the sponsor by the investigator. The event must be reported within 24 hours of when the investigator learns about it. Completing the serious adverse event form and reporting the event must not be delayed, even if not all the information is available. The investigator does not need to actively monitor patients for adverse events once this study has ended.

Serious adverse events occurring to a patient after the last administration of IMP of that patient has ended should be reported to the sponsor if the investigator becomes aware of them.

The serious adverse event form should be sent to the local safety officer (LSO) or designee (a contract research organization [CRO] in a country without a sponsor LSO) (contact information is in the Clinical Study Personnel Contact Information section); the LSO will forward the report to the sponsor's Global Patient Safety and Pharmacovigilance.

The following information should be provided to record the event accurately and completely:

- study number
- investigator and investigational center identification
- patient number
- onset date and detailed description of adverse event
- investigator's assessment of the relationship of the adverse event to the test IMP (no reasonable possibility, reasonable possibility)

Additional information includes:

- age and sex of patient
- date of first dose of IMP
- date and amount of last administered dose of IMP
- action taken
- outcome, if known

- severity
- explanation of assessment of relatedness
- concomitant medication (including doses, routes of administration, and regimens) and treatment of the event
- pertinent laboratory or other diagnostic test data
- medical history
- results of dechallenge/rechallenge, if known
- for an adverse event resulting in death
 - cause of death (whether or not the death was related to IMP)
 - autopsy findings (if available)

Each report of a serious adverse event will be reviewed and evaluated by the investigator and the sponsor to assess the nature of the event and the relationship of the event to the test IMP, study procedures, and to underlying disease.

Additional information (follow-up) about any serious adverse event unavailable at the initial reporting should be forwarded by the investigator within 24 hours of when it becomes known to the same address as the initial report.

For all countries, the sponsor's Global Patient Safety and Pharmacovigilance will distribute the Council for International Organizations of Medical Sciences (CIOMS) form/Extensible Markup Language (XML) file to the LSO/CRO for submission to the competent authorities, Independent Ethics Committee/Institutional Review Boards (IEC/IRBs), and investigators, according to regulations. The investigator must ensure that the IEC/IRB is also informed of the event, in accordance with national and local regulations.

Note: Although pregnancy is not a serious adverse event, the process for reporting a pregnancy is the same as that for reporting a serious adverse event, but using the pregnancy form (see Section 7.2).

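### Section 7.1.5.3.1 starts awareness-only SAE reporting at the last IMP dose, contradicting its own first paragraph and Sections 7.1.2 and 7.1.5, which run the reporting period to the end of follow-up

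*Protocol*

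**What the plan says.** Three protocol sections state when SAE reporting changes from an unconditional duty to a duty that depends on the investigator happening to learn of the event.

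- **Section 7.1.2** defines the recording period as "the time period from signature of the informed consent form (ICF) through the follow-up visit". SAEs inside that period must be recorded on the CRF and reported immediately on the SAE form. Only then comes the weaker rule, which is conditional on awareness: "Serious adverse events and adverse events of special interest occurring in a patient after the defined study period should be reported to the sponsor".
- **Section 7.1.5** says that for SAEs "the study period is defined for each patient as that time period from signature of the ICF to the end of the follow-up period". The weaker rule again starts afterwards: "Serious adverse events occurring in a patient after the end of the follow-up period should be reported to the sponsor" on awareness.
- **Section 7.1.5.3.1** opens by saying that "all serious adverse events that occur during the study, regardless of judged relationship to administration of the test IMP, must be reported to the sponsor", within 24 hours of the investigator learning of the event. It adds: "The investigator does not need to actively monitor patients for adverse events once this study has ended". The next paragraph applies the weaker rule to SAEs occurring "after the last administration of IMP of that patient has ended should be reported to the sponsor if the investigator becomes aware of them".

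Sections 7.1.2 and 7.1.5 both send the reader to Section 7.1.5.3.1 for the reporting procedure. Section 7.1.7 routes adverse events of special interest through the same process.

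**The concern.** The sentence in Section 7.1.5.3.1 is the outlier, and it sits in the section that sites consult when they file a report. It is also the only text there that addresses the period after a patient's last dose specifically. A site could reasonably take it as the rule for that period.

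This matters more here than in many studies. Long-term safety is the primary objective. There is no Data Monitoring Committee (Section 5.9.3) and there are no formal rules for early termination. Section 3.4 relies on review of SAEs as the centers report them, so the timeliness of those reports is the study's main safety oversight.

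The follow-up visit is also placed at about five half-lives after the last dose, so the interval affected is the one in which drug is being cleared. SAP Section 8.3 sets no end date for treatment-emergent events, so SAEs with onset after the last dose enter the SAE tables for treated patients.

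**Working it through.** **Size of the gap, treated patients.** Inputs are the last dose at week 36 (Section 3.1), the end-of-treatment visit at week 40, and the follow-up visit at week 68 ± 1 week (Table 4).

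- Last dose to follow-up visit: 68 − 36 = 32 weeks, or 31 to 33 weeks with the visit window.
- Check against the plan's stated interval of about 7.5 months: 7.5 × 365.25 / 12 / 7 = 32.6 weeks, within 3% of 32. The plan's own figure reproduces.
- Share of participation: 32 / 68 = 0.47. This is elapsed time between the two cut-offs, not a share of events.
- Longest stretch without a scheduled contact in that window: 68 − 40 = 28 weeks.

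**Follow-up-only patients.** Table 5 times their visit from the last dose in the pivotal study, and they receive no IMP in this study. The Section 7.1.5.3.1 cut-off therefore falls before they enter, and all of their participation lies after it. Section 9.1 plans approximately 240 such patients. Patients with chronic cluster headache who were asked to stop treatment and stay in follow-up pass the cut-off when they stop.

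**Where awareness-only reporting begins.**

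| Place | Start of awareness-only reporting |
|---|---|
| Section 7.1.2 | after the follow-up visit |
| Section 7.1.5 | after the end of follow-up |
| Section 7.1.5.3.1, first paragraph | not before the study ends |
| Section 7.1.5.3.1, next paragraph | after the patient's last IMP dose |

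**What governs ascertainment.** These places agree with each other:

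- Section 7.1.2 requires patients to be questioned at each contact.
- Table 4 has an adverse event inquiry at weeks 40 and 68, and its footnote i runs recording to the end of participation.
- Table 5 and Appendix B have an inquiry at both visits for follow-up-only patients, with unscheduled visits for any safety concern.
- SAP Section 8.3 collects adverse events to the end of participation.

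So one sentence conflicts with everything else, and the conflict concerns sending SAE reports to the sponsor, not whether patients are asked.

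**After the fix.** The interval during participation under awareness-only reporting falls from about 32 weeks to 0 for a treated completer, and from the whole of participation to 0 for a follow-up-only patient.

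**The case against.** The strongest case on the other side is that this is an editorial slip with little practical effect. Sections 7.1.2 and 7.1.5 define the period, and they cite Section 7.1.5.3.1 only for procedure. Its first paragraph keeps the unconditional duty. Inquiry and CRF recording continue to the follow-up visit. An SAE disclosed at week 40 or week 68 is one the investigator is then aware of, so even the contested sentence calls for it to be reported.

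Most of this stands, and it limits the point. A reader might infer that SAE collection becomes passive for 47% of a treated patient's participation and for all of a follow-up-only patient's, and that SAE incidence is therefore biased downward. The documents do not support that:

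- The sentence does not tell sites to stop asking, and the inquiry and recording rules contradict that reading.
- The percentages measure time, not lost events. No SAE rate is given from which to compute a loss.
- For follow-up-only patients, SAP Section 8.3 provides only an overall adverse event presentation.
- The figure of 240 is a plan. SAP Section 2.1 records that the study completed in Q2/2019 after early termination of both pivotal studies.

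The objection does not remove the contradiction. Two instructions in one section still give different duties for the same event. Between week 40 and week 68 no scheduled visit brings an event to light, and a patient who misses visit 12 is never asked. It is in those situations that a site's reading of the sentence could decide whether and when a report is sent.

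**Conclusion.** The contradiction is real and lies in current protocol text. Section 7.1.5.3.1 disagrees with its own first paragraph and with Sections 7.1.2 and 7.1.5 on when awareness-only SAE reporting begins. The disagreement spans about 32 weeks for a full-course treated patient, assuming the scheduled last dose and follow-up visit, and the whole participation of a follow-up-only patient.

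The consequence is ambiguous, late or missing expedited reports, concentrated between weeks 40 and 68 and in patients without visit 12. It is not passive ascertainment throughout. Whether the SAE counts are affected at all depends on how sites read the sentence and on an event rate that the documents do not give. The correction should be made because it is a stated safety-reporting rule in a study whose oversight rests on those reports.

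**What to change.** In Section 7.1.5.3.1, change the starting point of the awareness-only sentence from the patient's last IMP administration to the end of the follow-up period, so that it matches Sections 7.1.2 and 7.1.5. The cost is one sentence and a reminder to sites. No visit or assessment is added, and the 28-week interval between visits 11 and 12 is unchanged.

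If the protocol can no longer be amended, reconcile all SAEs with onset after the last dose between the CRF and safety databases, and disclose the inconsistency in the study report. That uses data already held. It can find events recorded but not reported, or reported late. It cannot find events that were never disclosed, for example in patients who missed visit 12, and the report should say so.
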